The Early Childhood Oral Health Impact Scale (ECOHIS) will be used to assess changes in OHRQL from baseline to completion of study. ECOHIS is a validated tool for use with parents/caregivers of children < 72 months of age. It consists of 13 questions grouped into two sections: 1) child impact, and 2) family impact. The child impact section includes nine questions in four areas: 1) symptoms, 2) functions, 3) psychology, and 4) self-image and social interaction. The family impact component covers two areas: 1) parental distress and 2) family function. Each question is scored from 0 to 5 [0= never, 1= hardly ever, 2= occasionally, 3 = often, 4= very often, 5= don't know]. A total score for each child is calculated by summing up response codes. The ECOHIS will allow us to calculate and compare mean ECOHIS scores at each visit and between groups. Our team has experience with analyzing ECOHIS.

Clinical outcomes assessed will include the proportion of teeth arrested (i.e., "arrest rate" = total number teeth arrested / total number of teeth treated), the proportion of children with any arrested caries, associated morbidity (dental pain and, dental abscess assessed using the PUFA index), and proportion of children requiring dental surgery under GA. The PUFA index is a score of the consequences of severely decayed teeth with visible pulpal involvement (P/p), ulceration caused by dislocated tooth fragments (U/u), fistula (F/f) and abscess (A/a). We will also record dmft and dmfs scores for each child at baseline and at subsequent study visits. The dmft and dmfs scores are cumulative counts of the total number of primary teeth or surfaces decayed, missing due to, or filled because of caries.

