Our research staff will contact interested parents/caregivers and will inform them of the study objectives, eligibility criteria, and procedures. Children will undergo a dental screening by the principle investigator or a calibrated and trained dental examiner to determine whether children meet the clinical criteria for this study by having cavitated caries lesions involving dentin (i.e. ICDAS category 5 or 6). Since ECC is more common in disadvantaged populations, we will arrange for transportation (i.e., taxis) for participants. We also anticipate that some participants will be newcomers and will require interpreters. We will arrange for WRHA interpreters when needed. Visits will occur at the principle investigator's dental suite at CHRIM or at one of the community-based clinics.

Baseline visit: Following written informed consent, children will be randomly allocated into one of three groups using sealed envelopes to ensure random allocation. Parents/caregivers will complete the baseline questionnaire administered by interviewer. Children will undergo a dental examination (without x-rays) to record the number of teeth and tooth surfaces with caries meeting ICDAS 5 or 6 criteria and the specific tooth numbers. We will record the location, size, hardness, colour, and activity status of each eligible caries lesion. We will also assess the total number of primary teeth and tooth surfaces affected by caries (i.e., dmft and dmfs). We will also determine the PUFA index. SDF will then be applied with a microbrush for one minute to each cavitated lesion meeting the eligibility criteria followed by 5% NaFV.

Second visit: Depending on the regimen children will return 4 months (Regimen 1), 6 months (Regimen 2), or 1 month (Regimen 3) later for their first follow-up visit and second application of SDF. Parents/caregivers will complete the ECOHIS tool. Prior to the second application of SDF, caries lesions that received the first application of SDF will be assessed to determine if caries is arresting. Lesions will be assessed for colour change, size, and hardness. Clinical data will be recorded including dmft, dmfs, and PUFA scores will be recorded. Following the dental assessment of the lesions under investigation, SDF will be applied to these lesions for one minute followed by 5% NaFV.

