Third visit: Depending on the regimen children will return 4 months (Regimen 1), 6 months (Regimen 2), or 1 month (Regimen 3) later for their final follow-up visit. Parents/caregivers will complete a follow-up questionnaire administered by interviewer. Caries lesions that were treated with applications of SDF will be assessed to see if caries is arrested. Caries lesions will be assessed for colour change, size, and clinical hardness. We will also record dmft, dmfs, and PUFA scores. Clinical data will be recorded on the Clinical Record Form.

Clinical data from baseline and each follow-up visit will be linked with questionnaire data. Data will be entered into a REDCap database and saved on the secure server at CHRIM.

Oral Microbiome Sub-Study: SDF may inactivate cariogenic bacteria in vitro. There was only one study that conducted RNA analysis of plaque in six children before and after treatment (3 receiving SDF and 3 placebo) reporting no changes in relative abundance of cariogenic bacteria. In that study, not only was sample size a major limitation, but the lead author is a director of Advantage Arrest™. Our proposal to assess 30 children would provide statistical power and help elucidate if SDF leads to changes in the oral bacteriome and mycobiome. This will provide novel insights into SDF's mechanism of action, whether antimicrobial, remineralization, or both. Ten children from each regimen will have plaque samples collected. Samples will be obtained at baseline (prior to SDF application), at the first follow-up visit (prior to SDF application), and at the final visit. Nucleic acid isolation from plaque samples will be done using the DNeasy

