PowerSoil Kit (Qiagen). It allows the isolation of genomic DNA (gDNA) from fungi and Gram (+-) bacteria, which will be used for downstream analyses. For the 16S rRNA (bacteriome) and ITS1 rRNA (mycobiome) amplicon sequencing, isolated gDNA will be used for PCR amplification of the V4 region of the bacterial 16S rRNA gene, and for PCR amplification of the fungal Internal Transcribe Spacer 1 (ITS1) rRNA gene. gDNA will be sequenced at Génome Québec using paired-end Illumina MiSeq PE250 sequencing. Data analysis will be performed in the [name] lab using established methods. Briefly, demultiplexed raw sequencing results will be filtered and clustered into operational taxonomic units (OTUs) and alpha and beta diversity analyses performed using QIIME2 (Quantitative Insights into Microbial Ecology) v. 2018.11. 16S sequences will be aligned and taxonomy assigned with the HOMD database. ITS1 sequences will be aligned and taxonomy assigned with the UNITE database.

Data Analysis:

This study will estimate the success of different SDF. Descriptive statistics will be used (e.g. frequencies, proportions, and means \pm standard Deviations). The “arrest rate” (primary outcome) will be calculated for the second visit and again at the third and final visit. Bivariate analyses will assess changes in clinical measures and survey data from baseline to the follow-up. McNemar’s test will be used to compare the arrest rate between the second and third clinical visits and to compare dichotomous data from the baseline questionnaire with that from the follow-up questionnaire within each regimen. Chi-squared analysis will compare arrest rates between the regimen groups. Paired t-test will be used to compare normally distributed interval data from the baseline questionnaire with that from the follow-up questionnaire within regimens (Mann-Whitney test if not normally distributed). We will rely on repeated measures analysis of variance to assess changes in ECOHIS scores and other continuous data over time (i.e. baseline vs. second visit vs. final study visit) within each regimen group and to assess differences between regimen groups. Although this is a pilot RCT, we will explore potential changes in the oral microbiome of those randomized to different regimens. This will provide insights into potential mechanisms of SDF action, whether it has antimicrobial activity and influences the oral microbiome composition. A p value ≤ 0.05 will be significant.

Ethics:

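### Changes in dmft/dmfs and GA surgery are compared per child although children are observed for 8, 12 or 2 months by regimen, so equal monthly rates can look like regimen differences (minor)

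*Combined protocol and SAP*

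**What the plan says.** Under Implementation, children "return 4 months (Regimen 1), 6 months (Regimen 2), or 1 month (Regimen 3) later for their first follow-up visit", and after that visit "return 4 months (Regimen 1), 6 months (Regimen 2), or 1 month (Regimen 3) later for their final follow-up visit". No total follow-up is stated. Adding the two intervals gives 8, 12 and 2 months.

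Under Instrumentation and Outcome Measures, the clinical outcomes include the "proportion of children requiring dental surgery under GA". The same section says "We will also record dmft and dmfs scores for each child at baseline and at subsequent study visits", and calls these scores "cumulative counts of the total number of primary teeth or surfaces decayed, missing due to, or filled because of caries".

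The Data Analysis section plans "repeated measures analysis of variance to assess changes in ECOHIS scores and other continuous data over time", with baseline, second visit and final visit as the time points, "within each regimen group and to assess differences between regimen groups". It names no analysis specifically for dmft, dmfs or GA surgery. Chi-squared is named for arrest rates only. Nowhere is there a rate per child-month, an offset, a time-to-event analysis or a common time of comparison.

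**The concern.** A cumulative count, or the proportion of children who have had an event, tends to rise with the time watched. Here that time is set by the regimen. If the visits are treated as the same three time points in every arm, the final visit means month 8, month 12 or month 2. Regimen 3 would then tend to look best and Regimen 2 worst on new caries and GA surgery, even if neither regimen changed the monthly rate.

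The Significance section says the trial should show which regimen is most effective and should inform a larger trial. A regimen ranking on these outcomes that came from length of observation could carry over into that design. Unlike arrest, which is a state at a visit, these outcomes have a usable denominator in child-months, and the plan does not use it.

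**Working it through.** **The plan's own figure.** The documents give no total follow-up, no dmft increment and no GA rate. The stated design figure that enters here is the group size. With 22 evaluable children and 20% loss, 22 / (1 − 0.20) = 27.5, rounded up to 28. This agrees with the plan, so 22 per arm is used below.

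**Time observed** (Second visit and Third visit paragraphs).
- Regimen 1: 4 + 4 = 8 months; 22 × 8 = 176 child-months.
- Regimen 2: 6 + 6 = 12 months; 22 × 12 = 264 child-months.
- Regimen 3: 1 + 1 = 2 months; 22 × 2 = 44 child-months.

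**Change in dmft.** With a common monthly rate r, the expected change is r × t, so the ratio is 8:12:2 = 4:6:1. At an assumed r = 0.05 the means are 0.4, 0.6 and 0.1. Divided by months observed, all three return 0.05.

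**Total dmft.** Assume a baseline mean of 6; the pilot's average of six lesions per child is only a proxy for this. The Regimen 2 to Regimen 3 ratio of final totals is then:
- r = 0.05: (6 + 0.6) / (6 + 0.1) = 1.08
- r = 0.10: (6 + 1.2) / (6 + 0.2) = 1.16
- r = 0.20: (6 + 2.4) / (6 + 0.4) = 1.31

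**False rejection with no difference in monthly rates.** Simulated with 22 per arm, alpha 0.05, and overdispersed gamma-Poisson increments (shape 1, assumed). The baseline mean is 6, with an SD of about 4.9 in the main-effect run. The rates are assumptions.

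| New dmft per month | ANOVA of change | Regimen-by-visit test | Regimen main effect on totals |
|---|---|---|---|
| 0.02 | about 20% | about 26% | 4.9% |
| 0.05 | about 50% | about 59% | 4.6% |
| 0.10 | about 76% | about 84% | 5.6% |

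The regimen-by-visit test used uncorrected degrees of freedom, which may explain part of its margin over the ANOVA of change. Under the same model, a robust Poisson comparison with a log(months) offset rejected in about 4%, 6% and 6%. Those figures are for trials with at least one event in every arm, which at 0.02 per month was only about 56% of trials.

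**GA surgery.** With a common monthly hazard h, the proportion is 1 − exp(−h × t).

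| h per month (assumed) | Regimen 1 | Regimen 2 | Regimen 3 | Regimen 2 / Regimen 3 |
|---|---|---|---|---|
| 0.01 | 7.7% | 11.3% | 2.0% | 5.7 |
| 0.02 | 14.8% | 21.3% | 3.9% | 5.4 |
| 0.05 | 33.0% | 45.1% | 9.5% | 4.7 |

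Regimen 3 expects 44 × 0.02 = 0.88 GA events at 2% per month, so the chance of none is exp(−0.88) = 41%. At 1% per month it is exp(−0.44) = 64%.

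**The case against.** The strongest reply is that the plan does not commit itself to the comparison that goes wrong. It records total scores, defines no increment, does not name a regimen-by-visit term, and places dmft/dmfs under continuous data only by inference. If the regimen main effect on totals is what is read, the test holds its level. All of this stands, and it limits the point. It does not remove it, because the stated purpose of the ANOVA is to assess changes over time and differences between regimens. The interaction is the natural term for that question, and it cancels the baseline level.

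A reader might infer three stronger things that the documents do not support.
- That the plan's dmft scores would differ six-fold. Six-fold applies to change from baseline only; totals differ by about 1.1 to 1.3-fold over 0.05 to 0.20 new dmft per month. For GA proportions, six is approached only when events are rare.
- That a planned test of GA surgery would reject too often. No between-regimen test is named for it, and the ANOVA is for continuous data. For GA surgery the weakness is how the outcome is expressed.
- That this undermines the primary outcome. Arrest is not an event rate, and nothing here bears on it.

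It is also fair to object that this is a pilot sized on arrest rate, that dmft, dmfs and GA surgery are in none of its objectives, and that a model with an offset may have no finite Regimen 3 estimate. These objections hold. They set the severity and shape the remedy.

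**Conclusion.** The point holds in limited form and is minor. The unequal observation time and the absence of any adjustment follow directly from the documents. The 4:6:1 ratio is exact for expected change under a constant, equal monthly rate. The false-rejection figures (about 26% to 84% for regimen-by-visit) rest on three assumptions: 0.02 to 0.10 new dmft per month, the overdispersion model, and dmft being analysed as continuous data with the interaction or the change being read. The GA proportions rest on an assumed constant hazard, and they illustrate a crude comparison, not a planned test.

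**What to change.** In the Data Analysis section:

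1. For between-regimen comparison, replace the visit-label ANOVA of dmft/dmfs with change from baseline to last visit per child-month. Compare regimens by Poisson or negative binomial regression with robust errors and offset log(months observed). Say how a negative change is handled, since a count model cannot take one.
2. Report GA surgeries per child-month with exact confidence intervals. Make any comparison exact or penalised, because Regimen 3 may have no events and an ordinary regression would then have no finite estimate.
3. State that crude increments and GA proportions are not comparable between regimens.

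The cost is SAP wording and simple analyses that use visit dates. No change to visits or data collection is needed. The downside is that the offset assumes a roughly constant monthly rate. This is doubtful for GA surgery, because some children are recruited from a surgery wait list and their timing may follow the queue. With 44 child-months, the Regimen 3 interval will be wide, and the report should say so.

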Arrest of caries lesions will be determined by assessing clinical hardness, colour change, and size of lesions at baseline, at second visit, and at the final study visit. Children will be recruited and we will perform block randomization by site in order to achieve equal proportions in each regimen by clinic site of recruitment. Study visits will occur at the Children's Hospital Research Institute of Manitoba (CHRIM) or at community-based dental clinics. Following informed consent the child's parent/caregiver will complete a short questionnaire (via interview) on general and dental health, oral hygiene, dietary intake of sugars, and family demographics along with the ECOHIS to assess OHRQL. SDF will be applied on the day of recruitment to cavitated lesions involving dentin followed by 5% NaFV. Depending on which frequency regimen children are randomized to, they will return for a second visit. During this second visit, caries lesions treated with SDF at baseline will be assessed to see if caries is arrested as determined through measures of hardness, colour change, and size. At this same visit a second application of SDF will be applied to these initially treated caries lesions followed by 5% NaFV. Children and parents will return for the third and final study visit according to the schedule of their randomized grouping. Parents/caregivers will complete a follow-up questionnaire similar to the

baseline tool. Caries lesions previously treated by SDF will be assessed for clinical hardness, colour change and size to determine if they have arrested.

Population: As ECC is age specific, participants will be < 72 months of age with active caries and their parents/caregivers. The majority will be recruited from community-based dental clinics in Winnipeg (i.e., Access Downtown, Mount Carmel Clinic, and SMILE Plus Children's Dental Clinic) or who are currently on a wait list for dental surgery under general anesthesia in Winnipeg. We found that these were ideal sites for our recently completed feasibility trial of SDF. We will restrict participation to children living in the Winnipeg region or within a one hour drive of Winnipeg to minimize the risk of loss-to-follow-up. Eligibility criteria are designed to select young children who have active caries, and thus are at an increased risk of morbidity from existing caries and onset of new caries.

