Inclusion Criteria: 1) Child is < 72 months of age with ECC with active caries lesions; 2) Child has ≥ 1 primary tooth with caries that is eligible to receive SDF. Eligible primary teeth must: a) have soft cavitated caries lesions extending into dentin (ICDAS 5 or 6); b) the cavitated lesions must allow for direct application of SDF. Teeth that meet any of the PUFA criteria (i.e. spontaneous pain due to caries, pulp exposure, mobility, signs of pulpal infection such as abscess, fistula, or swelling) will be excluded. However, a child would still be eligible even if they have at least one tooth that meets PUFA criteria, but other eligible teeth with caries do not.

Exclusion Criteria: 1) Child is allergic or has sensitivity to silver or other heavy metal ions; 2) Child has hereditary generalized developmental defects of enamel (e.g., amelogenesis imperfecta, dentinogenesis imperfecta); 3) Child has severe medical problems that limit participation; 4) Child requires immediate rehabilitation under general anesthesia because of severe infection or pain; 5) Antibiotic use within the last 2 weeks (for the microbiome sub-study).

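### On the natural reading, allocation comes before the eligible teeth are charted, so the arrest-rate denominator can be chosen with the regimen known; lock the tooth list first and make it the denominator

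*Combined protocol and SAP*

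**What the plan says.** The Baseline visit paragraph (under Implementation) opens with allocation: "Following written informed consent, children will be randomly allocated into one of three groups using sealed envelopes to ensure random allocation". It then describes the parent questionnaire, a dental examination that notes the affected teeth by number, and the lesion record: "We will record the location, size, hardness, colour, and activity status of each eligible caries lesion". The dmft, dmfs and PUFA scores come next, and the paragraph ends with treatment: "SDF will then be applied with a microbrush for one minute to each cavitated lesion meeting the eligibility criteria".

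A dental screening is described before this visit. Its stated purpose is "to determine whether children meet the clinical criteria for this study by having cavitated caries lesions involving dentin". It is not said to produce a tooth list.

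Inclusion Criteria set conditions for each tooth. The lesion must be soft, cavitated and into dentin (ICDAS 5 or 6), and "the cavitated lesions must allow for direct application of SDF". Teeth with a PUFA sign are left out, but "a child would still be eligible even if they have at least one tooth that meets PUFA criteria", provided that other teeth qualify.

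The Design text (under Methods) ties follow-up to the baseline set: at the second visit "a second application of SDF will be applied to these initially treated caries lesions". Instrumentation and Outcome Measures defines the arrest rate as teeth arrested divided by teeth treated. Data Analysis makes it the primary outcome, calculates it at both follow-up visits and compares it between regimens by chi-squared test.

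No section says that the baseline examiner is unaware of the allocation, or that the envelope stays closed until charting is finished.

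**The concern.** Sealed envelopes protect the assignment of children to regimens. They do not protect the choice of teeth within a child who has already been assigned. Here the unit of the primary outcome is the tooth, and a child who passes screening may still have some teeth that enter and others that do not. Softness, access and PUFA signs have to be judged tooth by tooth.

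If those calls are made with the regimen known, borderline teeth could be admitted more readily in one regimen than in another. The baseline set is the one treated again and assessed later, so a difference at this step carries through to the arrest rate at both follow-up visits. A chi-squared comparison would not reveal it.

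**Working it through.** **1. Order of steps.** As written, the baseline visit runs: consent, envelope, questionnaire, examination with tooth numbers, lesion record, dmft/dmfs, PUFA, SDF. The Design text does not place randomization relative to the examination, so it neither confirms nor contradicts this order.

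**2. The plan's own figures.** From Sample and Justification of Sample Size: 3 × 22 × 6 = 396 lesions. The half-width 1.96 × √(0.5 × 0.5/400) = 4.9 points agrees with the stated ±5.0%. For drop-out, 22/0.80 = 27.5, rounded up to 28 per group. None of these depends on the order of steps.

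**3. Illustration of size.** Taken from the plan: 22 × 6 = 132 lesions per regimen, and arrest rates p of 80% and 96% as the ends of its range of similar benefit. Assumed: an intermediate rate of 90%; one lesion per tooth (the sample size counts lesions, the arrest rate counts teeth); omission in one regimen only; and a fraction f = 10% to 25% of the lesions that would not arrest left off the list.

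- Lesions omitted: k = f × (1 − p) × 132.
- Rate if every omitted lesion would have failed: p / [1 − f(1 − p)].
- Rate if half of the same k would have arrested: (132p − k/2) / (132 − k).

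| p | k | Rate, all omitted would fail | Shift (points) | Rate, half would arrest | Shift (points) |
|---|---|---|---|---|---|
| 80% | 2.6–6.6 | 81.6–84.2% | 1.6–4.2 | 80.6–81.6% | 0.6–1.6 |
| 90% | 1.3–3.3 | 90.9–92.3% | 0.9–2.3 | 90.4–91.0% | 0.4–1.0 |
| 96% | 0.5–1.3 | 96.4–97.0% | 0.4–1.0 | 96.2–96.5% | 0.2–0.5 |

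If omitted lesions arrest like the rest, the shift is zero. For these omission fractions the first shift column is an upper figure, because an examiner cannot know at baseline which lesions will fail.

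**4. Scale.** The 95% half-width for one regimen, 1.96 × √[p(1 − p)/132], is 6.8 points at 80% and 3.3 at 96% if lesions are independent. With six lesions per child and an assumed intracluster correlation of 0.1 to 0.3, it is multiplied by √(1 + 5 × ICC), that is √1.5 to √2.5. This gives 8.4–10.8 points at 80% and 4.1–5.3 at 96%. The shifts in the table at those two rates lie inside these half-widths. That does not make a bias harmless, since an interval describes random error, but it keeps the size in proportion.

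**5. Sensitivity to the assumptions.** Suppose instead that 10–30% of lesions are hard to arrest, that these arrest at 50–80% against 96% for the rest, and that one regimen leaves off 25–100% of them. The shift then runs from 0.4 to 13.8 points. With 20% hard lesions and half of them left off, it is 1.4 points if they arrest at 80% and 4.1 if they arrest at 50%. The 13.8 needs every one of a 30% hard group, arresting at 50%, to be left off: 96 − (0.7 × 96 + 0.3 × 50) = 13.8. No input of this second set except the 96% is in the documents.

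**The case against.** The strongest reply is that sentence order is weak evidence of procedural order. The only explicit markers in the paragraph are that allocation follows consent and that SDF comes after the charting. The paragraph is not strictly sequential either: it records eligible lesions before it mentions PUFA, although PUFA is part of tooth eligibility. This stands. The order is the natural reading, not a stated rule.

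The second reply is that the route is narrow. Eligibility follows set criteria, every lesion that meets them is to be treated, the first application is the same in all regimens, and the stated hypothesis is similar arrest rates. This stands too, and it is why the effect may be close to zero. It narrows the room for judgement about softness, access and PUFA without closing it.

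Third, moving the envelope alone would not secure the denominator. SDF would still be applied after the envelope is opened, so a listed tooth left untreated would drop out of teeth treated. This is correct, and the remedy must cover it.

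A reader might also infer that nothing before treatment needs the allocation, because the Design text first uses the regimen to set the return date: "Depending on which frequency regimen children are randomized to, they will return for a second visit". That goes too far. The Oral Microbiome Sub-Study takes plaque from ten children per regimen before SDF, so the allocation may be needed before that sample.

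**Conclusion.** The point holds as a gap in the written procedure. On the natural reading, the set of teeth behind the primary outcome can be chosen after allocation, and nothing in the plan masks the person who chooses it. The size of any bias cannot be derived from the documents and may be small. The figures above rest on assumed omission in one regimen only. The case for change is that the protection costs little, not that a large bias has been shown.

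Three stronger readings are tempting, and the documents support none of them:

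- **That the examiner knows the regimen.** The plan is silent on this.
- **That the selection of children is open to influence.** Screening for child eligibility is described before the envelope step; the exposure is which teeth enter.
- **That baseline grades shifted by knowledge of the regimen would change the arrest count.** The plan gives no basis for that claim, and none is made here.

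**What to change.** In the Baseline visit paragraph, put the steps in this order: consent; questionnaire; examination, PUFA and lesion charting; a signed and timed list of study teeth with their baseline grades, then locked; the next envelope opened; first SDF application. If practice already follows this order, the text should say so.

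In Instrumentation and Outcome Measures and in Data Analysis, define the arrest-rate denominator as the teeth on the locked list. Report any listed tooth left untreated, with the reason.

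The cost is one new signed record and a reordering of steps within the same visit. Sample size and the number of visits do not change. Plaque samples that depend on regimen would be taken after the envelope is opened and before SDF, and so after the examination, in the same way for all regimens. The sub-study text should state this.

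The change does not address unmasked assessment of lesions at the second and third visits, which needs its own provision.
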